6.6.2. Pembrolizumab Dose Delays and Discontinuation

Adverse events (both nonserious and serious) associated with pembrolizumab exposure may represent an immunologic etiology. These AEs may occur shortly after the first dose or several months after the last dose of treatment. Pembrolizumab must be withheld (dose reductions are not permitted) for drug-related toxicities and severe or life-threatening AEs. See Section 6.9.1.3 for supportive care guidelines, including use of corticosteroids. [Table JVDF.5](#) presents the guidelines for treatment delays and discontinuation of pembrolizumab for specific AEs associated with pembrolizumab treatment.

Table JVDF.5. Pembrolizumab Treatment Discontinuation Guidelines for Specific Adverse Events at Least Possibly Related to Pembrolizumab

	Adverse Event	CTCAE Grade	Treatment Delay and Discontinuation
1	Diarrhea/Colitis	2-3	
Delay pembrolizumab until resolved to Grade 0-1.
 
 • If resolved to Grade 0-1 within 12 weeks of last dose, then resume pembrolizumab. • Within 12 weeks of last dose, if toxicity does not resolve to Grade 0-1 *or* with inability to reduce corticosteroid to ≤ 10 mg/day of prednisone or equivalent per within 12 weeks, discontinue pembrolizumab.
		4	Immediately and permanently discontinue pembrolizumab.
2	Increased AST, ALT, or Bilirubin^a	2	
Delay pembrolizumab until resolved to Grade 0-1.
 
 • If resolved to Grade 0-1 within 12 weeks of last dose, then resume pembrolizumab. • If NOT resolved to Grade 0-1 within 12 weeks of last dose, then discontinue pembrolizumab.
		3-4	Immediately and permanently discontinue pembrolizumab. See exceptions below.
3	Type 1 Diabetes Mellitus (if new onset) or Hyperglycemia associated with evidence of beta cell failure	T1DM or 3-4	
Delay pembrolizumab until patients are clinically and metabolically stable.
 
 • If clinically and metabolically within 12 weeks of last dose, then resume pembrolizumab. • If NOT clinically and metabolically stable within 12 weeks of last dose, then immediately and permanently discontinue pembrolizumab.
4	Hypophysitis	2-4	
Delay pembrolizumab until resolved to Grade 0-1.
 
 • If resolved to Grade 0-1 within 12 weeks of last dose, then resume pembrolizumab. • Within 12 weeks of last dose, if toxicity does not resolve to Grade 0-1 *or* with inability to reduce corticosteroid to ≤ 10 mg/day of prednisone or equivalent per within 12 weeks, immediately and permanently discontinue pembrolizumab.

Pembrolizumab Treatment Discontinuation Guidelines for Specific Adverse Events at Least Possibly Related to Pembrolizumab (continued)

	Adverse Event	CTCAE Grade	Treatment Delay and Discontinuation
5	Hyperthyroidism	2	Therapy with pembrolizumab can be continued; non-selective beta-blockers (e.g., propranolol) are suggested as initial therapy for hyperthyroidism (Section 6.9.1.3.5).
		3	
Delay pembrolizumab until resolved to Grade 0-1.
 
 • If resolved to Grade 0-1 within 12 weeks of last dose, then resume pembrolizumab. • Within 12 weeks of last dose, if toxicity does not resolve to Grade 0-1 *or* with inability to reduce corticosteroid to ≤ 10 mg/day of prednisone or equivalent per within 12 weeks, immediately and permanently discontinue pembrolizumab.
		4	
 • Immediately and permanently discontinue pembrolizumab.
	Hypothyroidism	2-4	Therapy with pembrolizumab can be continued while treatment for the thyroid disorder is instituted.
6	Infusion Reaction	2	
 • First occurrence: Stop infusion of pembrolizumab until resolved to Grade 0-1. 
 ◦ If resolved to Grade 0-1 within 1 hour of stopping infusion, then restart infusion at 50% of the original rate (e.g., from 100 mL/hr to 50 mL/hr). ◦ If NOT resolved to Grade 0-1 within 1 hour of stopping infusion, delay pembrolizumab until symptoms resolve, and premedicate for the next scheduled dose. • Second occurrence: If toxicity develops despite premedication, immediately and permanently discontinue pembrolizumab.
		3-4	Immediately and permanently discontinue pembrolizumab.

Pembrolizumab Treatment Discontinuation Guidelines for Specific Adverse Events at Least Possibly Related to Pembrolizumab (continued)

	Adverse Event	CTCAE Grade	Treatment Delay and Discontinuation
7	Pneumonitis	2	
Delay pembrolizumab until resolved to Grade 0-1.
 
 • If resolved to Grade 0-1 within 12 weeks of last dose, then resume pembrolizumab. 
Within 12 weeks of last dose, if toxicity does not resolve to Grade 0-1 *or* with inability to reduce corticosteroid to ≤ 10 mg/day of prednisone or equivalent per within 12 weeks, immediately and permanently discontinue pembrolizumab.

		3-4	Immediately and permanently discontinue pembrolizumab.
8	Renal Failure or Nephritis	2	
Delay pembrolizumab until resolved to Grade 0-1.
 
 • If resolved to Grade 0-1 within 12 weeks of last dose, then resume pembrolizumab. • Within 12 weeks of last dose, if toxicity does not resolve to Grade 0-1 *or* with inability to reduce corticosteroid to ≤ 10 mg/day of prednisone or equivalent per within 12 weeks, immediately and permanently discontinue pembrolizumab.
		3-4	Immediately and permanently discontinue pembrolizumab.
9	Other Adverse Events^b	3 or severe	
Delay pembrolizumab until resolved to Grade 0-1.
 
 • If resolved to Grade 0-1 within 12 weeks of last dose, then resume pembrolizumab. • Within 12 weeks of last dose, if toxicity does not resolve to Grade 0-1 *or* with inability to reduce corticosteroid to ≤ 10 mg/day of prednisone or equivalent per within 12 weeks, immediately and permanently discontinue pembrolizumab.
		4	Immediately and permanently discontinue pembrolizumab.

Pembrolizumab Treatment Discontinuation Guidelines for Specific Adverse Events at Least Possibly Related to Pembrolizumab (concluded)

Abbreviations: AE = adverse event; ALT = alanine aminotransferase; AST = aspartate aminotransferase; CTCAE = Common Terminology Criteria for Adverse Events; T1DM = type 1 diabetes mellitus.

Note: Permanently discontinue for any severe or Grade 3 drug-related AE that recurs or any life-threatening event. Reoccurrence of Grade 2 pneumonitis also warrants permanent discontinuation.

- a For patients with liver metastasis who begin treatment with Grade 2 AST or ALT, if AST or ALT increases by greater than or equal to 50% relative to baseline and lasts for at least 1 week, then patients should be discontinued.
- b Patients with intolerable or persistent Grade 2 drug-related AE(s) may hold study medication at physician discretion. Permanently discontinue pembrolizumab for persistent Grade 2 adverse reactions for which pembrolizumab has been held, that do not recover to Grade 0-1 within 12 weeks of the last dose.

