6.9.1.3. Supportive Care for Pembrolizumab

Supportive care guidelines for the management of specific AEs with potential immunologic etiology are outlined below. Where appropriate, these guidelines include the use of oral or intravenous treatment with corticosteroids as well as additional anti-inflammatory agents if symptoms do not improve with administration of corticosteroids. Several courses of steroid tapering may be necessary, as symptoms may worsen when the steroid dose is decreased. For each disorder, attempts should be made to rule out other causes such as metastatic disease or bacterial or viral infection, which might require additional supportive care. The treatment guidelines are intended to be applied when the investigator determines the events to be related to pembrolizumab.

If after the evaluation the event is determined not to be related, the investigator does not need to follow the treatment guidance as outlined below.

It may be necessary to perform conditional procedures such as bronchoscopy, endoscopy, or skin photography as part of evaluation of the event.

6.9.1.3.1. *Pneumonitis - Pembrolizumab*

Apply the following supportive care guidance for pneumonitis:

For Grade 2 events, treat with systemic corticosteroids (prednisone 1 to 2 mg/kg/day or equivalent). When symptoms improve to Grade 0-1, steroid taper should start and be continued over no less than 4 weeks.

For Grade 3-4 events, immediately treat with intravenous steroids (methylprednisolone 125 mg followed by high-dose oral steroids (prednisone 1 to 2 mg/kg/day or dexamethasone 4 mg every 4 hours). Administer additional anti-inflammatory measures, as needed.

Add prophylactic antibiotics for opportunistic infections, in the case of prolonged steroid administration.

6.9.1.3.2. *Diarrhea/Colitis - Pembrolizumab*

Patients should be monitored carefully for signs and symptoms of enterocolitis (such as diarrhea, abdominal pain, and blood or mucus in stool, with or without fever) and of bowel perforation (such as peritoneal signs and ileus).

- All patients who experience diarrhea/colitis should be advised to drink liberal quantities of clear fluids. If sufficient oral fluid intake is not feasible, fluid and electrolytes should be substituted via IV infusion. For Grade 2 or higher diarrhea, consider GI consultation and endoscopy to confirm or rule out colitis.
- For **Grade 2 diarrhea/colitis**, administer oral corticosteroids (prednisone 1 to 2 mg/kg/day or equivalent).

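### In six rows of Table JVDF.5 the restart rule ignores steroid dose but the stop rule does not, so a patient at Grade 0-1 and above 10 mg/day prednisone at week 12 meets both

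*Protocol*

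**What the plan says.** Table JVDF.5 in Protocol Section 6.6.2 gives delay and discontinuation rules for events at least possibly related to pembrolizumab. Six rows share one structure:

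- diarrhea/colitis, Grade 2-3
- hypophysitis, Grade 2-4
- hyperthyroidism, Grade 3
- pneumonitis, Grade 2
- renal failure or nephritis, Grade 2
- other adverse events, Grade 3 or severe

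Each cell opens with "Delay pembrolizumab until resolved to Grade 0-1". A restart bullet follows: "If resolved to Grade 0-1 within 12 weeks of last dose, then resume pembrolizumab". The last bullet stops the drug if the toxicity has not reached Grade 0-1 in that time, or, as an alternative trigger, on steroid dose. In the diarrhea/colitis row the steroid limb reads "with inability to reduce corticosteroid to ≤ 10 mg/day of prednisone or equivalent per within 12 weeks, discontinue pembrolizumab". In the other five it reads "with inability to reduce corticosteroid to ≤ 10 mg/day of prednisone or equivalent per within 12 weeks, immediately and permanently discontinue pembrolizumab".

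The table note makes any recurrent severe or Grade 3 related event a permanent stop, and adds "Reoccurrence of Grade 2 pneumonitis also warrants permanent discontinuation".

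Section 6.9.1.3 gives the steroid treatment. For Grade 2 pneumonitis the instruction is to "treat with systemic corticosteroids (prednisone 1 to 2 mg/kg/day or equivalent"), and "When symptoms improve to Grade 0-1, steroid taper should start and be continued over no less than 4 weeks". For Grade 2 diarrhea/colitis it is to "administer oral corticosteroids (prednisone 1 to 2 mg/kg/day or equivalent"). Grade 3 diarrhea/colitis starts with intravenous methylprednisolone, followed by oral prednisone in the same mg/kg range or dexamethasone. Diarrhea/colitis has the same minimum taper, starting at Grade 1 or less.

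**The concern.** The delay line and the restart bullet look only at grade. The stop bullet looks at grade and steroid dose. Two things follow.

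First, the restart and stop rules overlap. At week 12 a patient whose event has settled to Grade 0-1 but who is still above 10 mg/day satisfies both, and two sites could treat identical patients in opposite ways.

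Second, before week 12 the stop bullet has not yet come into play, so grade is the only restart condition. Where the protocol's steroid guidance is followed, a patient first reaches Grade 0-1 when the taper begins, which is when the steroid dose is still high. Section 6.9.1.3 itself warns that symptoms can return as the steroid is reduced, so Grade 0-1 at that point may not last.

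Safety and tolerability is the primary objective. Because recurrence of Grade 2 pneumonitis, or of a severe or Grade 3 related event, costs the patient the drug for good, a premature restart can do harm and also end treatment. Dose delays and discontinuations are reported as well, and they would partly reflect how each site read the table.

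**Working it through.** **Logic of the six cells.** Let R mean that the toxicity reached Grade 0-1 within 12 weeks of the last dose. Let S mean that corticosteroid was reduced to 10 mg/day prednisone or less within 12 weeks. As written, restart = R, and stop = (not R) or (not S).

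| Grade 0-1 (R) | ≤10 mg/day (S) | Restart rule | Stop rule |
|---|---|---|---|
| yes | yes | met | not met |
| yes | no | **met** | **met** |
| no | yes | not met | met |
| no | no | not met | met |

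One of the four combinations meets both rules. If restart becomes R and S, it is the exact complement of stop, and the overlap falls to 0 of 4. The Grade 2 AST/ALT/bilirubin row shows the contrast: its restart and stop bullets both test grade alone, so they are already complements.

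**Is it resolved elsewhere?** The table note and footnotes a and b add no steroid condition to restart and set no order of precedence. Section 6.6 encourages resumption within 21 days where possible and appropriate, preferably on the next Day 1, and mentions no steroid limit. Attachment 7 allows systemic glucocorticoids for suspected immune events and sets no ceiling for restarting.

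**Steroid dose when Grade 0-1 is reached** (diarrhea/colitis and Grade 2 pneumonitis only; no dose is stated for the other four rows). The guidance is 1 to 2 mg/kg/day.

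- Even 1 mg/kg/day exceeds 10 mg/day for any patient over 10 kg.
- Assumed weight 50 to 100 kg: 50 × 1 = 50 mg/day to 100 × 2 = 200 mg/day.
- Relative to the threshold: 50/10 = 5 to 200/10 = 20 times, at the start of the taper.

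**Dose at an actual restart.** On schedule, the next Day 1 is at most 21 days after Grade 0-1 is reached. The minimum taper is 4 × 7 = 28 days, so at least 28 − 21 = 7 days of it remain. The protocol does not set the taper's shape. As an illustration, assume a linear 28-day taper to zero:

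- Dose on day 21: 50 × (1 − 21/28) = 12.5 mg/day to 200 × (1 − 21/28) = 50 mg/day, or 1.25 to 5 times the threshold. An earlier Day 1 gives a higher dose.

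**When the week-12 overlap arises.** Twelve weeks is 84 days.

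- A 28-day taper cannot be completed by day 84 if Grade 0-1 is reached after day 84 − 28 = 56. Only those still above 10 mg/day on day 84 meet both bullets.
- On the linear illustration, 10 mg/day is reached after 28 × (1 − 10/50) = 22.4 days to 28 × (1 − 10/200) = 26.6 days. The cut-off then moves to day 84 − 26.6 = 57.4 to day 84 − 22.4 = 61.6. A slower taper moves it earlier.

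**The case against.** The strongest reply is that each cell has a natural reading. The stop bullet is the more specific and more cautious, and in five of the six rows it orders immediate and permanent discontinuation. A site applying the whole cell at week 12 would stop. That is probably the intent, but the table does not say so, and this reading settles only the week-12 case.

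It can also be said that the 10 mg/day limb is a 12-week deadline, not a ceiling on the dose at restart. This is right: restarting at week 5 in mid-taper contradicts no other line of the table. The earlier problem is a missing safeguard, and only the week-12 overlap is a contradiction. Still, the sponsor judged steroid dose relevant enough to end treatment, and left it out of the decision to resume treatment.

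The objections on size are fair. The 5-to-20-fold figure describes the start of the taper, and the dose at restart may be much closer to the threshold. Day 56 marks the last day from which a minimum taper can be completed by week 12, not the exact boundary of the overlap. A patient restarted early never reaches week 12 from the original last dose, so the two problems largely affect different patients. Frequency is unknown.

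Investigator discretion also stands: the table is called guidelines, Section 6.6 qualifies resumption, and the investigator may discontinue a patient at any time. So no restart is compelled. Discretion does not supply the missing restart criterion, though. The week-12 overlap cannot affect the 21-day DLT assessment, but it can affect later adverse events and discontinuations.

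**Conclusion.** The point holds. Six rows contain a restart rule and a stop rule that are both met by a patient at Grade 0-1 and above 10 mg/day prednisone at week 12, and no other part of the protocol resolves it. This rests on the text alone. In the same rows, steroid dose plays no part in the restart decision before week 12.

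The dose figures apply only to diarrhea/colitis and Grade 2 pneumonitis. They rest on an assumed 50 to 100 kg body weight and, for the restart-day figures, on an assumed linear taper and on-schedule cycles. How many patients would be affected cannot be estimated from the documents. No sample size, power, alpha or analysis method changes. The ambiguity is in a dosing rule in a study whose primary objective is safety, and it should be corrected.

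**What to change.** In each of the six rows, put both conditions into the restart bullet, for example: *Resume pembrolizumab if toxicity is Grade 0-1 and corticosteroid is at or below 10 mg/day prednisone or equivalent, both reached within 12 weeks of the last dose; otherwise discontinue.* Give the opening delay line the same two conditions. The threshold is the protocol's own, and the restart and stop rules then become exact complements.

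The cost is a wording change to one table at the next protocol amendment, with no new procedure or assessment. Some patients still tapering will restart later, and a few more may be discontinued.

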Creatinine OR Measured or calculated creatinine clearance (see Attachment 5)	$\leq 1.5 \times \text{ULN}$ OR $\geq 60 \text{ mL/min}$
Hepatic	
Total bilirubin	$\leq 1.5 \times \text{ULN}$
AST (SGOT) and ALT (SGPT)	$\leq 2.5 \times \text{ULN}$ OR $\leq 5 \times \text{ULN}$ for patients with liver metastases
Coagulation^b	
International Normalized Ratio (INR) or Prothrombin Time (PT)	INR $\leq 1.5 \times \text{ULN}$ or PT ≤ 5 seconds above ULN unless patient is receiving anticoagulant therapy as long as INR or PT is within therapeutic range of intended use of anticoagulants
Partial Thromboplastin Time (PTT) or Activated Partial Thromboplastin Time (aPTT)	PTT or aPTT ≤ 5 seconds above ULN unless patient is receiving anticoagulant therapy as long as PTT or aPTT is within therapeutic range of intended use of anticoagulants
Thyroid	
TSH, T3, and T4	TSH within the normal limits OR Total T3 or free T3 and free T4 are within the normal limits.

Abbreviations: ALT = alanine aminotransferase; aPTT = activated partial thromboplastin time; AST = aspartate aminotransferase; INR = international normalized ratio; PT = prothrombin time; PTT = partial thromboplastin time; TSH = thyroid-stimulating hormone; ULN = upper limit of normal.

^a Creatinine clearance should be calculated per institutional standard.

^b Patients on full-dose anticoagulation must be on a stable dose (minimum duration 14 days) of oral anticoagulant or low molecular weight heparin. If receiving warfarin, the patient must have an INR ≤ 3.0 and no active bleeding (i.e., no bleeding within 14 days prior to first dose of study treatment) or pathological condition present that carries a high risk of bleeding (e.g., tumor involving major vessels or known varices). Patients on anticoagulation therapy with unresected primary tumors or local tumor recurrence following resection are not eligible.

[8] Be males or females at least 18 years of age on day of signing informed consent

[9] Have an anticipated life expectancy of ≥ 3 months

- [10] Have resolution, except where otherwise stated in the inclusion criteria, of all clinically significant toxic effects of prior systemic cancer therapy, surgery, or radiotherapy to Grade ≤ 1 by National Cancer Institute (NCI) Common Terminology Criteria for Adverse Events (CTCAE), Version 4.0 (v 4.0)

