13.b	Adverse Event	4	
Permanently discontinue treatment immediately, with the exception of Grade 4 fever or Grade 4 laboratory abnormality, in which case:
 
 • First occurrence: Delay ramucirumab until resolved to Grade 0-1. 
 ◦ If resolved to Grade 0-1, may resume ramucirumab original dose at the discretion of the investigator. ◦ If NOT resolved to Grade 0-1 within a reasonable timeframe, discontinue ramucirumab at investigator's discretion. • Second occurrence: Delay ramucirumab until resolved to Grade 0-1. 
 ◦ If resolved to Grade 0-1, reduce ramucirumab dose. ◦ If NOT resolved to Grade 0-1 within a reasonable timeframe, discontinue ramucirumab at investigator's discretion.

Dose-Modification Guidelines for Ramucirumab for Adverse Events at least Possibly Related to Ramucirumab, including Adverse Events of Special Interest (concluded)

Abbreviations: AESI = adverse event of special interest; CTCAE = Common Terminology Criteria for Adverse Events; NCI = National Cancer Institute.

- a Perform urinalysis within 3 days prior to each infusion of ramucirumab. If 24-hour urine collection is also performed, the results of 24-hour urine collection should be used for clinical decision-making.
- b Patients who enter the study with symptoms or laboratory values equivalent to NCI-CTCAE Version 4.0 Grade 1-2 adverse events should not necessarily have dose delays or reductions related to the persistence or mild worsening of those symptoms or laboratory values. Grade 2 toxicities which represent clinically significant worsening of symptoms from baseline, ramucirumab dose may be delayed at the discretion of the investigator. If the toxicity is resolved to Grade 0-1, may reduce ramucirumab dose. If the toxicity is not resolved to Grade 0-1, may discontinue ramucirumab.

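### Table JVDF.5 gives two unreconciled pembrolizumab stop conditions for patients with liver metastases who start at Grade 2 AST or ALT

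*Protocol*

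**What the plan says.** **Entry.** In Protocol Section 5.1, criterion [7], the AST/ALT limit is 2.5 x ULN, raised to 5 x ULN "for patients with liver metastases".

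**Pembrolizumab rules.** Table JVDF.5 (Section 6.6.2) is titled "Pembrolizumab Treatment Discontinuation Guidelines for Specific Adverse Events at Least Possibly Related to Pembrolizumab", so it covers related events only. Row 2 is labelled "Increased AST, ALT, or Bilirubin^a", with the footnote marker on the row label.
- Grade 2 line: delay until Grade 0-1, and resume if that level is reached by 12 weeks after the last dose. Otherwise: "If NOT resolved to Grade 0-1 within 12 weeks of last dose, then discontinue pembrolizumab". Return to baseline is not offered as an alternative.
- Grade 3-4 line: "Immediately and permanently discontinue pembrolizumab. See exceptions below". The Grade 2 line has no such pointer.
- Footnote a opens "For patients with liver metastasis who begin treatment with Grade 2 AST or ALT" and discontinues these patients on a rise of at least 50% over baseline that persists for at least a week. It says nothing about delay or resumption.

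**Related text.** The liver note in the DLT definition (Protocol Section 6.1.1.1.1; SAP Section 5.2.1.1) uses the same 50% threshold, with 7 days, for the same subgroup. Section 6.9.1.3.6 has Grade 2 hepatic events monitored until values are back to baseline, but starts the steroid taper at Grade 1 or less.

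**The concern.** Row 2 measures recovery on an absolute grade scale, while footnote a measures worsening against the patient's own baseline. For most patients the two scales do not collide. For a patient who starts at Grade 2 they do: Grade 0-1 is better than the value at which the protocol let the patient in, so complete recovery to entry status does not meet the written restart condition.

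Two things are at stake. An eligible patient could lose one of the two study drugs although the enzymes are back where they began. And sites could treat the same course differently in good faith, depending on how they read the footnote. Safety and tolerability is the primary objective. The SAP reports dose modifications with reasons and dose intensity (Section 5.3.6) and lists adverse events leading to discontinuation (Section 5.3.8). In cohorts of 15 to 25 patients, even a few delays or stops that depend on how the table is read would show in those outputs.

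**Working it through.** The plan states no figure on this point, so there is none to reproduce. The check sets the provisions side by side and then sizes the gap between restart level and baseline.

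**Step 1. What each reading implies for a related rise below 50% in this subgroup**

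| Reading of footnote a | Value stays in Grade 2 | Value reaches Grade 3 |
|---|---|---|
| Adds to both grade lines | Delay; discontinue if Grade 0-1 is not reached by 12 weeks, even if back at baseline | Stop under the Grade 3-4 line |
| Replaces both grade lines | Not stopped; no hold or restart level written | Not stopped; no hold or restart level written |
| Exception in the Grade 3-4 cell only | Delay; discontinue as in the first row | Not stopped; no hold or restart level written |

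The marker on the row label supports the second reading. The position of the pointer, in the Grade 3-4 cell alone, gives some support to the third. The footnote is worded as a further reason to stop, which is compatible with the first.

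**Step 2. How far below baseline the restart level lies**

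The documents do not give the grade cut-offs. Assumption: the upper limit of Grade 1 is between 2.5 and 3 x ULN, and the upper limit of Grade 2 is 5 x ULN, equal to the entry cap.

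Fall needed to reach Grade 0-1 = 1 - (Grade 1 limit / baseline). Footnote a level = 1.5 x baseline.

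| Baseline (x ULN) | Fall needed, limit 3 | Fall needed, limit 2.5 | Footnote a level (x ULN) |
|---|---|---|---|
| 3.5 | 1 - 3/3.5 = 14.3% | 1 - 2.5/3.5 = 28.6% | 5.25 |
| 4 | 1 - 3/4 = 25% | 1 - 2.5/4 = 37.5% | 6.0 |
| 5 | 1 - 3/5 = 40% | 1 - 2.5/5 = 50% | 7.5 |

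So the same patient entering at 4 x ULN faces a footnote threshold 50% above baseline and a restart level 25% to 37.5% below it.

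**Step 3. Does the arithmetic show which reading was meant?**

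A 50% rise passes 5 x ULN for any baseline above 5/1.5 = 3.33 x ULN, where the Grade 3-4 line would already stop treatment. A purely additive footnote would therefore be redundant over (5 - 3.33)/(5 - 2.5) = 67% to (5 - 3.33)/(5 - 3) = 83% of the assumed Grade 2 range. This favours reading the footnote as a special rule for the subgroup. It rests on assumed cut-offs, and it does not supply the missing hold and restart levels.

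**The case against.** The strongest reply is that footnote a already governs the whole row. Its marker is on the row label, the DLT definition repeats its 50% threshold, and an additive reading would make it redundant over most of the Grade 2 range. On that view a small rise does not lead to discontinuation. This has force: discontinuation after a small rise is one possible result of the text, not an established one. What remains is that the footnote does not say that it overrides the Grade 2 line, and that it states no delay or resumption level if it does.

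Other limits also stand.
- It is open whether a rise within Grade 2 triggers row 2 at all. SAP Section 5.2.1.3 counts an event as treatment-emergent when it first occurs or worsens in severity, while Protocol Section 8.2.1 has any change in a preexisting condition recorded.
- Hepatic handling is also referred to a site guidance document that is not among the documents reviewed and may address this.
- A reader might infer that Table JVDF.4 already has the baseline rule missing here, since its footnote b says that patients entering with Grade 1-2 values "should not necessarily have dose delays or reductions related to the persistence or mild worsening of those symptoms or laboratory values". That softens the trigger for persistent or mildly worse values. It is attached to the row for other ramucirumab-related events and itself uses Grade 0-1 as the recovery level, so it supplies no baseline restart level.

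**Conclusion.** The inconsistency is real but narrow. Row 2 and its footnote give different stop conditions for a subgroup that the protocol admits and names, and the text does not say which governs. On the additive reading, full recovery to the entry value after a related rise below 50% within Grade 2 can still end in discontinuation of pembrolizumab. On the replacement reading, delay and resumption are undefined for the subgroup.

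Three stronger inferences are not supported.
- A reader might conclude that a small rise means a permanent stop. The Grade 2 line says discontinue. The word permanently appears in the Grade 3-4 line and in footnote b, and footnote b belongs to the row for other adverse events.
- A reader might contrast a patient whose small rise stays in Grade 2 and is stopped with one whose equal rise reaches Grade 3 and is spared. That outcome needs the third reading in the working and is not demonstrated.
- A reader might put a number on the patients affected. The documents give no share entering at Grade 2, so any count would rest on an invented proportion.

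The distances below baseline (25% to 37.5% at 4 x ULN, 40% to 50% at 5 x ULN) depend on the assumed cut-offs. That Grade 0-1 lies below a Grade 2 baseline does not. The effect on dose intensity cannot be quantified from the documents, and no sample-size or power figure is affected.

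**What to change.** Reconcile both grade lines of row 2, footnote a and inclusion criterion [7] in one footnote to Table JVDF.5. For patients who enter with Grade 2 AST or ALT, it should say which provision governs delay, which governs resumption and which governs discontinuation, and whether the exception applies to the Grade 2 line as well as the Grade 3-4 line. The sponsor's clinical team chooses the rule; no threshold is proposed here. The site guidance document on hepatic monitoring should be checked for agreement with the result.

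The cost is one footnote at the next amendment. No analysis or sample-size text needs to change.
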